A full understanding of etiology and diagnosis of peri-implant diseases is crucial for finding effective treatments for these diseases that are more widely accessible to dentists. Several treatment protocols for peri-implant diseases have been proposed, but no gold standard has been established to date. Thus, the purpose of this study was to analyze efficacy of stabilized chlorine dioxide as a chemical adjuvant for treatment of peri-implant mucositis in a non-surgical treatment protocol with a 3-month follow-up. A collection swab was performed for microbiome analysis of the mouth on three visits.

[3] Study Design

Fifty-four individuals with peri-implant mucositis were identified to participate in this study and randomized into two groups to analyze clinical parameters and results of this study: 1) test group (stabilized chlorine dioxide rinse) and 2) control group (placebo). Each group was associated with periodontal basic therapy.

Treatment Protocol

After inclusion of the patients, medical history and initial examination were performed, patients were randomly divided into the following two groups: 1) test (stabilized chlorine dioxide rinse associated with periodontal basic therapy); and 2) control (placebo associated with periodontal basic therapy).

Periodontal basic therapy consisted of oral hygiene instruction, motivation, retentive factor removal, and an adaptation of the protocol of full-mouth scaling and root planing (stabilized chlorine dioxide mouthwash will be used). Plastic currets were used to instrument the implants, and metal currets to instrument teeth. Immediately after instrumentation, chemical solutions of chlorine dioxide or placebo were dispensed to the subjects.

The subjects followed their normal oral-hygiene procedures with the addition of using the study rinse toothbrush and toothpaste provided to them.

Overview of the Sample Collection Protocol for Microbiome Analysis

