6. Performed a Turesky modification of the Quigley-Hein Plaque Index (PI) grading on all natural teeth and implants in the dentition.
7. Assessed bleeding on probing (BOP) on all natural teeth and implants in the dentition.
8. Verified data capture.
9. X-rays
10. Full mouth Scaling
11. Randomization and dispensation of the Oral Hygiene Kit and Oral Hygiene Diary.
12. The subjects then followed their normal oral-hygiene procedures with the addition of using the study rinse, toothbrush, and toothpaste provided to them.
13. Provided diary for recording use of product rinse or placebo.
14. Provided supplies for 14 days (day 1 to day 14 of the study). Weighed and recorded the weight of test rinse or placebo, as applicable, being provided.
15. Instructed Subject to bring remaining oral rinse or placebo bottle
16. Scheduled following appointments for Visit 2 (2 weeks after base line) and Visit 3 (3 months) and noted in their study instructions and diary. Subjects were to be seen within plus or minus 7 days.

VISIT 2 - INTERIM EXAMINATION - DAY 14

This examination took place within 14 calendar days after Baseline Examination (Visit 1) \pm 3 days. The following procedures were conducted:

1. Reviewed any change in medical and dental history
2. Rinsed mouth with water and collected samples for microbiome analysis by using a cotton swab on the inside of the cheek and tongue mucosa.
3. Evaluated extra- and intra- oral areas for any mucosal irritation or pathology.
4. Performed a Modified Gingival Index (MGI) grading on all natural teeth and implants in the dentition.
5. Performed a Turesky modification of the Quigley-Hein Plaque Index (PI) grading on all natural teeth and implants in the dentition.
6. Weighed and recorded remaining test rinse or placebo as applicable.
7. Checked record for use of test rinse or placebo in the diary.
8. Provided diary for recording use of product rinse or placebo.
9. Provided supplies for 30 days (day 15 to day 45 of the study). Weighed and recorded the weight of test rinse or placebo, as applicable, being provided.
10. Confirmed appointment date scheduled for the Compliance Visit (Visit 3). The subjects were given a reminder call 2 - 3 days prior to their scheduled appointment.

VISIT 3 – COMPLIANCE VISIT – DAY 45

This examination took place within 45 calendar days after Baseline Examination (Visit 1) \pm 7 days. The following procedures were conducted:

1. Weighed and recorded remaining test rinse or placebo as applicable.

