2. Checked record for use of test rinse or placebo in the diary.
3. Provided diary for recording use of product rinse or placebo.
4. Provided supplies for remaining 45 days (day 46 to day 90 of the study). Weighed and recorded the weight of test rinse or placebo, as applicable, being provided.
5. Confirmed appointment date scheduled for the Final Examination Visit (Visit 4). The subjects were given a reminder call 2 - 3 days prior to their scheduled appointment.

VISIT 4 - FINAL EXAMINATION – DAY 90

This examination took place within 90 days following the Baseline Examination (Visit 1) \pm 7 days. The following procedures were conducted:

1. Collected the subject's diary and unused products at check-in. All partially used products were assessed for volume remaining and recorded. Used products were retained until after a monitoring visit, and then returned to the Sponsor.
2. Performed pregnancy testing on females of childbearing age.
3. Rinsed mouth with water and collected samples for microbiome analysis by use of a cotton swab on the inside of the cheek and tongue mucosa.
4. Asked the subject to report any changes in medical or dental health since the last visit.
5. Evaluated extra- and intra- oral areas for any mucosal irritation or pathology.
6. Performed a Modified Gingival Index (MGI) grading on all natural teeth and implants in the dentition.
7. Performed a Turesky modification of the Quigley-Hein Index (PI) grading on all natural teeth and implants in the dentition.
8. Assessed bleeding on probing (BOP) and probing depth on all natural teeth and implants in the dentition.
9. X-rays
10. Weighed and recorded remaining test rinse or placebo as applicable.
11. Checked record for use of test rinse or placebo in the diary.

[10] Study Timeline

Using December 2018 as a calendar starting point, the entire month would provide 20 days for recruiting. As the screening, cleaning and baseline visit can be all on the same day we were considering that subjects could begin Study Visit 1 between January 2019 and December 2019. The final study visits was conducted in March 2020. A final report concluded by December 2020.

[11] Statistical Evaluation

The primary objective of this study was to analyze efficacy of stabilized chlorine dioxide as a chemical adjuvant for treatment of peri-implant mucositis in a non-surgical treatment protocol with a 3-month follow-up.

The primary objective was determined by an examination of the following data:

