Slope of probing depth, time 1 to 3	57	-1.47	0.015	-0.10632	0.323886
Slope of gingivitis index, time 1 to 3	57	-0.99	-0.03	-0.24351	0.221807
Slope of plaque score, time 1 to 3	57	-1.53	-0.045	-0.45254	0.358255
Valid N (listwise)	57				

Global Probing Depths (GPD)

Global probing depth (GPD) collected at the first visit did not differ significantly between groups; control group's (Group A) initial GPD was 2.76 (SEM = 0.092) interval, and 2.68 (0.071) for test group (Group X), a non-significant statistical difference ($p = 0.48$).

Neither did the GPD score differ between final visits of control group (Group A) (GPD = 2.64 (0.130) and test group (Group X) (GPDI = 2.37, (0.166), $t = 1.27$, $df = 55$, $p = 0.28$. Nonetheless, the GPD decreased significantly for control group (Group A), ($p = 0.028$; for X, $p < 0.001$) for both groups, but the group decreases were not significantly different from each other. Both mouthwashes reduced probing depth similarly.

The key signal of treatment effectiveness is a statistically significant treatment-by-time interaction, where improvement over time is greater for one treatment than another. Nearly parallel lines in Figure 2 and statistical testing indicated no appreciable and significant treatment-by-time interaction for GPD (See Figure 2, Figure 3).

Figure 2. Interaction plot showing that group assignment did not interact with time for probing depth.

[figure not shown]

Figure 3. Boxplots of probing depth results from treatment by control group (Group A) and test group (Group X). Probing depth was not affected differentially by the mouthwash treatments. Both conditions reduced probing depth slightly but not statistically significant.

Global Plaque Score

Control group (Group A) and test group (Group X) differed significantly in global plaque score (GPS) at initial assessment, requiring an additional analysis of covariance to confirm that a significant time by treatment interaction was not an artifact from the initial difference in GPS (See interaction plot, Figure 4, detailed in Figure 5). The test group's (Group X) initial average GPS was 3.00 (SEM = 0.071) versus 2.35 (0.097) for the control group (Group A), a significant difference ($t = -5.45$, $df = 50$, $p < 0.001$). At assessment 3, the last observation, the test group's (Group X) GPS (1.57, SEM = 0.110) was significantly lower than that for the control group (Group A); GPS = 1.98 (0.110), $t = 2.633$, $df = 55$, $p = 0.011$.

[figure not shown]

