There is a clear advantage to using ClōSYS® Ultra Sensitive oral rinse treatment (test rinse X) in terms of plaque and gingival index. In addition, ClōSYS® Ultra Sensitive oral rinse (test rinse X) appeared to have a preferential benefit for implant sites, over both control treatment (placebo rinse A) and over non-implant sites. The ClōSYS® Ultra Sensitive rinse (test rinse X) significantly reduced the plaque index and gingival index as compared to initial measures and those in control group (placebo rinse A) ($p < 0.001$). The observation of higher initial gingivitis scores for the ClōSYS® Ultra Sensitive oral rinse (test rinse X) did not affect the superiority of this test group treatment. In controlling for the inequality at baseline, and analysis of covariance showed the reduction of the plaque score remained significantly better in the ClōSYS® Ultra Sensitive oral rinse group (test rinse X) than for the control group (placebo rinse A) ($p < 0.001$). Also, using pre-post difference scores and slopes of the scores over time showed the treatment effect to be robust to the mismatch of initial levels of gingivitis and plaque ($P < 0.001$ for both).

Both groups improved from the use of mouthwashes, but the ClōSYS® Ultra Sensitive oral rinse (test rinse X) improved more and at a faster rate ($p < 0.001$) compared to the control group (placebo rinse A). There was no apparent effect on periodontitis between the two intervals in which it was measured.

Implant sites were significantly more ($p < 0.001$) and faster ($p < 0.001$) improved in the ClōSYS® Ultra Sensitive oral rinse group (test rinse X) than the other non-implanted teeth and in the control group (placebo rinse A).

Both ClōSYS® Ultra Sensitive oral rinse (test rinse X) and placebo rinse (rinse A) tested are safe to oral tissues and did not show any adverse effects.

Both ClōSYS® Ultra Sensitive oral rinse (test rinse X) and placebo rinse (rinse A) tested are safe to oral tissues and do not have any adverse effects.

Signature Page

[name]

Principal Investigator

[name] [name], PhD

REFERENCES

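### Two results sentences credit both arms' improvement to the mouthwashes, which a design without a no-rinse arm cannot support; separately, scaling is placed both before and after the Visit 1 indices

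*Combined protocol and SAP*

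**What the plan says.** **Attribution.** The Conclusions say "Both groups improved from the use of mouthwashes", then add that the test rinse group improved more and faster. The results under Global Probing Depths say "Both mouthwashes reduced probing depth similarly".

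**What both arms received.** Section 3, Treatment Protocol: "Periodontal basic therapy consisted of oral hygiene instruction, motivation, retentive factor removal", together with an adapted full-mouth scaling and root planing. Section 8 lists a toothbrush and toothpaste supplied to every subject. The comparator is a placebo rinse with the same ingredients apart from stabilized chlorine dioxide. There are two arms, and both rinse.

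**When scaling took place.**
- Section 4, schedule: the Scaling row is marked under Screening only. MGI and plaque index are first marked at Baseline.
- Section 5, synopsis item 6: screening and hygienic phase therapy fall in weeks -2 to -1, before Day 0.
- Section 9, Screening: no scaling step is listed.
- Section 9, Visit 1: MGI, plaque and BOP are steps 5 to 7; "Full mouth Scaling" is step 10; "Randomization and dispensation of the Oral Hygiene Kit and Oral Hygiene Diary" is step 11.
- Section 3: "Immediately after instrumentation, chemical solutions of chlorine dioxide or placebo were dispensed to the subjects".
- Section 10: "As the screening, cleaning and baseline visit can be all on the same day", with no statement of whether scoring came before or after cleaning.

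**The concern.** A reader of the two sentences would conclude that the placebo rinse worked, and that the whole of the test arm's fall came from rinsing. Within-arm change mixes scaling, instruction, the supplied brush and toothpaste, rinsing and regression to the mean. Randomization isolates one thing only: test rinse against placebo rinse, each on top of basic therapy.

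The document applies this standard itself. Under Global Probing Depths it calls a treatment-by-time interaction the key signal of effectiveness and reports none for that outcome. To say that both rinses reduced probing depth similarly then makes two claims without support: that each rinse caused a fall, and that the falls were alike.

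The scaling order matters for interpretation. MGI is the measure named for the primary objective. If its Visit 1 score was taken before scaling, the fall to Day 90 includes the scaling effect, and crediting that fall to a rinse overstates the rinse by more. The documents point both ways.

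**Working it through.** **1. Size of the within-arm falls credited to rinsing** (global scores, Results)

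| Outcome | Control | Test | Control fall / test fall |
|---|---|---|---|
| Probing depth | 2.76 - 2.64 = 0.12 | 2.68 - 2.37 = 0.31 | 39% |
| Plaque | 2.35 - 1.98 = 0.37 | 3.00 - 1.57 = 1.43 | 26% |
| Gingival index | 20.4% (1.91 x 0.204 = 0.39) | 27.3% (2.03 x 0.273 = 0.55) | 20.4/27.3 = 75% of the percentage fall |

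Tables 2 and 3 give a smaller control fall in gingival index. The overall fall is 1.972 - 1.485 = 0.487. The between-arm difference in fall, by the formula in step 2, is 2 x sqrt(0.485 x 0.0704) = 0.369. The control fall is then 0.487 - 0.369 x 30/57 = 0.29. The percentages imply a between-arm difference of only 0.55 - 0.39 = 0.16. The document does not reconcile 0.16 with 0.37, so the control fall is given as 0.29 to 0.39. None of these falls can be divided among their possible causes.

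**2. Is the probing-depth change shown to be similar?**

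Reproducing Table 2: F = 0.125 / (5.75/55) = 1.196 (printed 1.191, from a rounded mean square), p = 0.28.

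Arm sizes: error df 55 gives N = 57. With 27 controls, the test arm is 30 by subtraction. The Patients text says 26, and its implant counts add to 18 + 9 + 2 = 29, but neither added to 27 makes 57. Splits of 28/29 or 31/26 change the difference by less than 0.01.

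Table 3 slopes are half the total fall: (2.716 - 2.504)/2 = 0.106, as printed. So:
- difference in fall = 2 x sqrt(group SS x (1/27 + 1/30)) = 2 x sqrt(0.125 x 0.0704) = 0.188
- SE = 2 x sqrt((5.75/55) x 0.0704) = 0.172
- 95% CI = 0.188 ± 2.004 x 0.172 = -0.16 to 0.53

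The means in step 1 agree: 0.31 - 0.12 = 0.19. The upper limit exceeds the whole test-arm fall of 0.31, so the interval does not show similarity.

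**3. Why even this is provisional**

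Table 3 gives time-3 minima of 0 for all three measures. The minimum probing-depth slope, -1.47, equals a fall of 2.94, which fits a baseline of 2.94 followed by a recorded 0. A whole-mouth mean probing depth of 0 looks like a missing value stored as zero. That slope alone contributes (1.47 - 0.106)² = 1.86 of the corrected total SS of 5.875, or 32%.

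The tables do not say which arm it is in. As an illustration, drop that one slope. The arm mean slopes implied by step 2 are -0.151 (test) and -0.057 (control).
- If it is in the test arm: the test mean becomes (-0.151 x 30 + 1.47)/29 = -0.105, and the difference in fall is about 0.10 (95% CI -0.19 to 0.39).
- If it is in the control arm: the control mean becomes (-0.057 x 27 + 1.47)/26 = -0.003, and the difference is about 0.30 (0.02 to 0.58).

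The intervals remove the slope's own contribution from the error SS, leaving 3.95 or 3.68 on 54 df.

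**4. Scaling order, side by side**

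| Source | Scaling relative to Visit 1 MGI and plaque |
|---|---|
| Section 4 schedule | before |
| Section 5 synopsis (if hygienic phase therapy includes scaling) | before |
| Section 9 Visit 1 list | after (step 10 against steps 5 and 6) |
| Section 9 Screening list | no scaling at screening |
| Section 3 dispensing sentence | scaling immediately before dispensing; fits steps 10 and 11 |
| Section 10 | one day possible; scoring order not given |

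The Visit 1 order is the better supported, but no text says which governs. The effect of the order on the scores cannot be estimated from the documents.

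**The case against.** **The sentences are shorthand.** Each arm is defined as a rinse associated with basic therapy, so 'mouthwashes' could simply mean the arms. The probing-depth sentence follows a statement that the decreases did not differ significantly, and the Conclusions sentence goes on to a between-arm claim. This context is fair, and most of the efficacy claims in the Conclusions are between-arm. But the words as printed name the rinses as the cause, one sentence is in the Conclusions, and a non-significant difference is not similarity.

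**The order conflict is thin.** Screening and baseline may share a day. The schedule also marks BOP under Screening although Visit 1 step 7 scores it, so its columns are not a strict sequence. The synopsis counts only if hygienic phase therapy includes scaling, which is an inference. All of this stands and makes the Visit 1 order more likely. It does not remove the disagreement.

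**Randomization order.** A reader might infer a second conflict from section 3, where "patients were randomly divided into the following two groups" comes before basic therapy is described. The documents do not support that. It is paragraph order in a narrative that names the arms and then defines the therapy, whereas both explicit sequences, the schedule and the Visit 1 list, put scaling before randomization.

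**Baseline.** A reader might also infer that the baseline is undefined. It is defined: the synopsis calls the Visit 1 measurements the baseline examination, and the covariance analyses use the first-visit score. Only its position relative to scaling is unclear.

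**Conclusion.** The concern holds as a minor point of interpretation and documentation. Under any scaling order, the two sentences attribute to rinsing a change that the design cannot attribute. The placebo-arm falls affected are about 0.12 for probing depth, 0.37 for plaque and 0.29 to 0.39 for the gingival index. Similar probing-depth reduction is not shown: the difference in fall is 0.19 (-0.16 to 0.53). That interval assumes 57 analysed patients split 27/30 and takes the zero entries at face value.

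The schedule and synopsis conflict with the Visit 1 list on scaling. A reader might infer that this biases the treatment comparison. The documents do not show it: both arms had the same basic therapy, and nothing suggests that its timing differed by arm.

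A reader might also take the unadjusted Table 2 differences as the effect of the test rinse. They should not be used that way. The arms differed at Visit 1 on gingival index (p = 0.006) and plaque (p < 0.001), and the tables carry the unexplained zeros. The relevant quantity is the baseline-adjusted difference. For the gingival index it is reported only as t = 2.12, df = 51, p = 0.039, without an estimate.

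**What to change.** 1. Reword both sentences along the lines of: *both groups improved after periodontal basic therapy plus the assigned rinse*. For probing depth, write that *no between-arm difference was shown*.
2. Credit the test rinse only with the baseline-adjusted between-arm difference, reported with its estimate and 95% CI from the covariance analyses already run.
3. Before finalising those estimates and the probing-depth sentence, check the zero entries in Table 3 against source records. If they are missing values, recode them and rerun.
4. Correct the schedule and synopsis to the scaling order that site records confirm, and state whether the Visit 1 scores are pre- or post-scaling. No extra model term is needed.

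The cost is a few text corrections, a look at site records, output from existing models and, if the zeros prove to be missing values, one rerun. No new data collection is required.

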6. Study Duration and Visits: The study duration was (3 months) and was comprised of a total of 4 visits: Screening and hygienic phase therapy (weeks -2 to -1), Baseline (Visit 1, Day 0), Visit 2 (14 days), Visit 3 (45 days), Visit 4 (90 days).
7. Subjects received an Oral Hygiene Kit at Visit 1. The Modified Gingival Index (MGI), Bleeding on Probing (BOP) and Plaque Index (PI), Pocket depth and radiographs were measured, and all oral tissues examined (baseline examination). Subjects returned for Visit 2 in 14 days \pm 3 days to: 1) assess and record changes in indices and oral health and any adverse conditions. Visit 3 (45 days \pm 7) was a compliance visit for study drug utilization. Visit 4 (90 days \pm 7) was a repeat of Visit 1. Samples for microbiome analysis were collected at baseline (Visit 1), Day 14 (Visit 2), and Day 90 (Visit 4).
8. All parameters for clinical exam were calibrated between the examiners involved with the study.

[6] Study Materials (Oral Hygiene Kit)

STUDY DRUG

Both the active and placebo drugs were provided in liquid form, intended for oral administration. Sample products were labeled by the manufacturer and shipped directly to the site.

ADMINISTRATION

After tooth brushing in the morning and evening, the study product was administered orally using a cup that measures 15 mL of oral rinse, swishing in the oral cavity for 30 seconds and expectorating.

[7] Subjects

Subject recruitment occurred at the discretion of the Principal Investigator. After being recruited, potential subjects were informed of the purpose of the study and guided through HIPAA documentation and the informed consent process. Upon their understanding of the study, HIPAA regulations, and their agreement with the terms of the informed consent, subjects indicated so by signing the forms. The eligibility of potential subjects was determined through a series of screening interviews and an oral examination. Following screening, those potential subjects who retained eligibility were enrolled in the study at the discretion of the Principal Investigator. Approximately 75 subjects were screened to provide 54 enrollees. Once these subjects were randomized, study enrollment was complete.

Number of subjects: 54 subjects

Age: 18 years to 80 years

Gender: Both male and female subjects entered this study.

Remaining Natural Teeth: Minimum of 20

[8] Subject Eligibility Criteria

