Once a subject had been screened and qualified for study participation, that subject was enrolled and assigned the next available randomization number. The study randomization table was generated by a third-party statistician. This procedure was used to keep the Study Statistician blinded to subject treatments prior to database lock.

WITHDRAWAL

Subjects enrolled in the study were able to elect to withdraw at any time for any reason. Additionally, subjects were able to have been withdrawn from the study at the request of the Principal Investigator for the following reasons:

1. An adverse event required discontinuation of the study rinse in the judgment of the Principal Investigator or designee
2. Subject refused or failed to comply with the study protocol

3. There was a protocol violation(s) or deviation(s) that compromised the use of the subject's data

All patients withdrawn from the study by request or by the Principal Investigator were to be seen, if they consented, for a close-out evaluation. The reason for withdrawal would be recorded by the Principal Investigator or designee on the End of Study form. Patients who experienced complications and discontinued the study on their own were to be scheduled, if they consented, for an immediate follow-up/close-out examination to determine whether an adverse event was present, and if so, the causation of the adverse event was to be recorded. If treatment was needed for any adverse event causing withdrawal, the subject would be monitored until there was a return to normal conditions. (Every effort would be made to follow up with subjects who withdrew from the study.)

Test Product: ClōSYS® Ultra Sensitive Rinse

Placebo: Oral rinse comprising same ingredients as in test product except for stabilized chlorine dioxide.

Materials:

Sponsor shipped prelabelled 'Oral Rinse A' and 'Oral Rinse X' products to the Test Site. Both products were in 16 oz. size bottle and identical in appearance.

Each subject received the following supplies at Baseline (Visit 1) i.e. supplies for 0-14 days:

- a. 1 bottle (16oz) of either Oral Rinse A or Oral Rinse X))
- b. 35 measuring cups
- c. 1 tube of Crest Cavity Protection Toothpaste, Regular (8.2oz) and
- d. 1 ClōSYS toothbrush

Each subject received the following supplies at Visit 2 i.e. supplies for 15-45 days:

- a. 2 bottles (16oz) of either Oral Rinse A or Oral Rinse X)
- b. 70 measuring cups
- c. 2 tube of Crest Cavity Protection Toothpaste, Regular (8.2oz) and

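### No safety check is scheduled between Day 14 and Day 90, yet the conclusion on tissue safety carries no limit

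*Combined protocol and SAP*

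**What the plan says.** Section [9], Visit 3, lists five steps:

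1. the leftover rinse is put on the scale and its weight noted
2. "Checked record for use of test rinse or placebo in the diary"
3. a fresh diary is issued, described only as a log of rinsing
4. "Provided supplies for remaining 45 days (day 46 to day 90 of the study", with the weight dispensed recorded
5. the Visit 4 appointment is confirmed, with a reminder call beforehand

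The lead-in to that list calls the visit an examination ("This examination took place within 45 calendar days after Baseline Examination (Visit 1"), but no examination is among the steps. The synopsis (Section [5], item 7) says that Visit 3 "was a compliance visit for study drug utilization". The same item has Visit 2 record adverse conditions.

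The mucosal check is listed at Visits 2 and 4: "Evaluated extra- and intra- oral areas for any mucosal irritation or pathology". Visit 2 also reviews changes in medical and dental history. Visit 4 asks the patient about health changes since the previous visit.

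The Withdrawal text gives as one reason for removing a patient: "An adverse event required discontinuation of the study rinse in the judgment of the Principal Investigator or designee". It also offers a close-out evaluation to those who withdraw, and a prompt examination to those who stop on their own because of complications.

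The Conclusions state that both rinses are safe to oral tissues and without adverse effects. No time points are attached to that statement.

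**The concern.** Visit 3 is the only planned contact between Day 14 and Day 90, and half of the treatment period is still ahead when the next supply is handed out. The investigator may withdraw a patient for an adverse event, but no step at this visit is designed to bring one to notice. The diary is described only as a record of rinse use.

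Two things are at stake. First, irritation that begins after Day 14 and settles before Day 90, in a patient who keeps rinsing, falls outside every scheduled check in both arms. The unlimited safety conclusion therefore claims more than the scheduled data can support. Second, exclusion 5 bars systemic antibiotics throughout the study. Their use after Day 14 is next sought at Day 90, when recall is weakest.

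**Working it through.** **The plan's own figure.** Day 46 to Day 90 inclusive is 90 − 46 + 1 = 45 days, as stated for the Visit 3 supply.

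**Visits side by side** (schedule in Section [4]; steps in Section [9]).

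| Item | Visit 2 | Visit 3 | Visit 4 |
|---|---|---|---|
| Medical history update (schedule) | marked | blank | marked |
| Medications update (schedule) | marked | blank | marked |
| Oral examination (schedule) | marked | blank | marked |
| Question on health changes (steps) | step 1 | none | step 4 |
| Mucosal evaluation (steps) | step 3 | none | step 5 |
| Kit and diary | exchange | exchange | collection |

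Schedule, step list and synopsis agree, so the blank cells are the design and not a damaged table.

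**Length of the gap.** Inputs: Visit 2 at Day 14 ± 3, Visit 4 at Day 90 ± 7.
- Nominal: 90 − 14 = 76 days; 76/90 = 84% of the treatment period.
- Shortest within windows: (90 − 7) − (14 + 3) = 83 − 17 = 66 days.
- Longest within windows: (90 + 7) − (14 − 3) = 97 − 11 = 86 days.

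**Exposure in the gap.** Section [6] gives two rinses a day. 76 × 2 = 152 of 90 × 2 = 180 planned rinses, of which 45 × 2 = 90 follow the Day 45 dispensing.

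**Reach of the Visit 4 question.** It asks about changes since the previous visit. Taken literally, that is Visit 3, where no health question was put. The nominal stretch from Day 14 to Day 45 (45 − 14 = 31 days) is then covered by no question. The schedule also marks history and medication updates at Visit 4 without a recall period, and Visit 1 step 16 speaks of Visit 3 as the three-month visit. The intended reach is therefore unclear.

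**What a Day 45 check would gain.** It splits the 76 days into 45 − 14 = 31 and 90 − 45 = 45 days. Within the windows these run from 38 − 17 = 21 to 52 − 11 = 41 days, and from 83 − 52 = 31 to 97 − 38 = 59 days. The longest nominal gap falls from 76 to 45 days.

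**The case against.** The best defence is that this is a deliberate and consistent design. Visit 3 is a compliance visit, the product is spat out, the mucosa is examined at Day 14 and Day 90, and both arms are treated alike. There is also an unscheduled route: patients may withdraw at any time, those who stop with complications are to be offered prompt examination, and anyone treated for an adverse event that led to withdrawal is followed until recovery. All of this stands. It does not reach a patient who has a reaction, says nothing and carries on rinsing.

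Several stronger readings are tempting, and the documents do not support them.

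- A reader might infer that reactions in the gap could not be observed at all. Spontaneous report and the withdrawal route remain; what is missing is a scheduled check.
- A reader might infer that Visit 3 gathers nothing relevant. Weighing and the diary can show that a patient cut down on rinsing. They are not described as recording why.
- A reader might infer that NSAIDs were barred for the whole study. Exclusion 6 concerns chronic NSAID use and lacks the study-duration wording of exclusion 5.
- A reader might infer that safety over three months was claimed. The synopsis title mentions safety, and the conclusion mentions oral tissues, but neither gives a duration.
- A reader might take the 84% as what an added check would recover. It would not: gaps of 31 and 45 days would remain.

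The diary form and the patient instructions are not among the documents, so instructions to report symptoms can be neither shown nor ruled out. Nor do the documents say who staffs Visit 3, so the presence of someone able to examine the mouth cannot be assumed. Finally, the trial is complete, and only the wording of its conclusion can still be changed.

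**Conclusion.** The point holds as a limit on safety capture and on the safety conclusion. No history update, medication update, adverse-event question or oral examination is scheduled between Day 14 and Day 90: 76 days nominal, 66 to 86 within the windows. For patients who stay on the rinse, detection rests on what they volunteer or remember at Day 90. Systemic antibiotic use after Day 14 is likewise sought only at Day 90. The unlimited statement in the Conclusions goes further than this allows.

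This rests on taking the step lists and schedule as complete, and the diary as what the text describes. The rinse counts assume twice-daily use as planned. The documents do not show that any reaction was missed, nor that the gap biased the gingival index comparison. It is a modest improvement worth making, not a fault in the primary analysis.

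**What to change.** **Completed trial.** Limit the safety statement in the Conclusions, in both places where it appears, to findings at the Day 14 and Day 90 examinations plus events reported spontaneously. This is a change of wording only.

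**Any further use of the protocol.**
- Add to Visit 3, before dispensing, the Visit 2 review of medical and dental history and medications, with an open adverse-event question.
- Add the existing mucosal look at Visit 3 where an examiner is already present.
- Mark both in the Visit 3 column of the schedule, and bring the Visit 3 lead-in, which speaks of an examination, into line with its steps.
- Word the Visit 4 question to cover the time since the last health review.

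The cost is a few minutes at a visit that every patient is already due to attend, and more minor events to record and report. The few minutes are an assumption, since the documents give no visit durations. Where no examiner attends Visit 3, the mucosal look would cost more, and the history, medication and adverse-event questions can be adopted alone.
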